## **Inclusion Criteria:**

- 1. Age 5 to 65 years of age
- 2. **Diagnosis of WS** confirmed via genetic testing or a clinical diagnosis made by a clinician with significant experience treating patients with WS
- 3. Clinically significant anxiety as evidenced by a Pediatric Anxiety Rating Scale (PARS) score of 10 or greater (5-item scale). The PARS ("The Pediatric Anxiety Rating Scale (PARS): Development and psychometric properties." 2002) was chosen as an inclusion criterion (and outcome measure) since it assesses severity across common anxiety disorders in children including generalized anxiety, social anxiety, separation anxiety, and transition-associated anxiety. In addition, it is an instrument that allows the clinician to incorporate both child and parent report into a final clinician-rated score for each item.
- 4. A Clinical Global Impression Severity Item score ≥ 4 (moderate) for anxiety symptoms at Screen and Baseline.

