## **Outcome Measures:**

- 1. **Pediatric Anxiety Rating Scale (PARS)**. The PARS will be the primary outcome measure. It will be conducted at screening, baseline, and each follow-up visit.
- 2. Child and Adolescent Symptom Inventory (CASI) Anxiety Items. These include 20 parent-rated items from the Child and Adolescent Symptom Inventory. It will be conducted at baseline and each follow-up visit.
- 3. Screen for Childhood Anxiety Related Emotional Disorders (SCARED). The SCARED (Birmaher et al 1999) is a 41-item scale that includes both a child/self-report and parent-report form. It is used to screen for symptoms of panic disorder, separation anxiety disorder, social phobia, and generalized anxiety disorder, as well as school phobias. It will be conducted at baseline and each follow-up visit.

- 4. Aberrant Behavior Checklist (ABC-2). The ABC-2 is a 58-item questionnaire with 5 subscales derived by factor analysis: Irritability, Social Withdrawal, Stereotypy, Hyperactivity, and Inappropriate Speech. It has been extensively used in psychopharmacological studies of autism and other developmental disorders and assesses many symptoms that are either central to autism (Social Withdrawal, Stereotypy, Inappropriate Speech) or frequently a target of treatment (Irritability, Hyperactivity). It will be conducted at baseline and each follow-up visit.
- 5. **Pittsburgh Sleep Quality Index (PSQI).** The PSQI is a self-rated 19 item questionnaire which assesses sleep quality and disturbances over a one-month time interval (Buysse et al., 1989). It will be used to assess the sleep quality of study participants by parent/caregiver report.

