- 6. Clinical Global Impressions (CGI). A trained clinician will perform the CGI. The CGI is designed to take into account all factors to arrive at an assessment of severity and response to treatment, including parent report, parent-rated measures, and clinician-rated measures (as described below). The CGI Severity (CGI-S) item is rated on a scale from 1 to 7 (1 = normal, not at all ill; 2 = borderline ill; 3 = mildly ill; 4 = moderately ill; 5 = markedly ill; 6 = severely ill; 7 = among the most extremely ill patients). The CGI Global Improvement (CGI-I) item is also rated from 1 to 7 (1 = very much improved; 2 = much improved; 3 = minimally improved; 4 = no change; 5 = minimally worse; 6 = much worse; 7 = very much worse). Subjects receiving a CGI-I rating of 1 or 2 will be classified as **responders** to treatment. The severity ratings will be conducted at screen, baseline and the last follow-up visit. The improvement ratings will be conducted at each follow-up visit.

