#### **Statistical Analysis Plan:**

Demographic and clinical characteristics of the sample will be tabulated using means (SDs) for continuous characteristics and clinical scale scores treated as continuous and frequencies and percents for categorical and ordinal variables.

Change in PARS 5-item total score between baseline and week 16 will provide our primary preliminary estimate of efficacy. To estimate changes in PARS score and all other clinical outcomes but the CGI-I between baseline and week 16, we will use repeated measures linear regression models, as implemented in PROC MIXED in SAS and fit using REML estimation, with repeated measurements of clinical scores as outcomes and time, in categories, as the predictor. Our primary interest will be only in the difference between baseline and week 16 scores, but all observed scores will be included as outcomes, given that partially observed scores may be informative for estimation. We will obtain an estimate of 16-week change and corresponding 95% CI using a contrast of the week 16 and baseline model parameters. A contrast of the same parameters will provide a statistical test of the null hypothesis that there was no change in outcome between baseline and 16 weeks. For the CGI-I, we will estimate the percentage who respond to treatment and corresponding 95% CI using the proportion of participants with CGI-I scores <=2 at 16 weeks. For this calculation, participants who withdrew prior 16 weeks due to side effects will be included as non-responders, and participants who withdrew for other reasons will be excluded. Sensitivity to change will be compared between scales using standardized effect sizes, calculated using the estimated 16-week change in each outcome divided by the SD of the outcome at baseline. We will also tabulate and compare the percent of item-level missing data for each scale.

Frequency of all side effects and adverse events and corresponding 95% CIs will be tabulated. Tolerance and corresponding 95% CI will be estimated using the proportion of participants who did not withdraw from the study before 16 weeks due to reasons other than side effects or an adverse event who discontinue treatment due to side effects or an adverse event. We will also use the 16-week study retention rate and corresponding 95% CI, calculated as the proportion of the participants enrolling in the study who remain in the study for 16 weeks, as a measure of feasibility.

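### PARS and CGI-S carry entry minimums and the other scales do not, so ranking scales by change over baseline SD tends to favour those two; the documents do not fix by how much

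*Combined protocol and SAP*

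**What the plan says.** Aim 2 (Specific Aims) asks which anxiety measures are most useful. It judges them on three things: sensitivity to change, item-level missing data, and feedback from users. It sets no ranking rule.

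The Statistical Analysis Plan makes the first of these concrete: "Sensitivity to change will be compared between scales using standardized effect sizes", defined as the estimated "16-week change in each outcome divided by the SD of the outcome at baseline". The numerator comes from a repeated-measures model that keeps incomplete participants, because "partially observed scores may be informative for estimation". That model covers every clinical outcome except CGI-I, so CGI-S is included. The plan makes no allowance for the entry criteria and gives no interval for a difference between scales.

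Two outcomes also decide entry. Inclusion criterion 3 needs a "Pediatric Anxiety Rating Scale (PARS) score of 10 or greater (5-item scale"), with no visit named. Criterion 4 needs a CGI-S rating of at least 4 and does name the visits: "moderate) for anxiety symptoms at Screen and Baseline". Outcome Measures says of PARS: "It will be conducted at screening, baseline, and each follow-up visit". Either of two PARS scores could therefore be the qualifying one. SCARED, CASI Anxiety, ABC-2 and PSQI have no minimum and are first collected at baseline (Schedule of Measures, Table 1).

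**The concern.** A standardised effect size compares scales fairly only if its denominator means the same thing for each. Here the baseline SD is taken in a sample selected on two of the scales. Selection truncates those two directly and the others only through their correlation with them. CGI-S is the clearest case: "The CGI Severity (CGI-S) item is rated on a scale from 1 to 7", but only 4 to 7 can occur at baseline.

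The numerator moves the same way. People admitted for a high score on a scale tend to score lower on it later without any treatment effect, and that drift is weaker on a scale not used for selection.

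At stake is one of the three Aim 2 criteria. PARS or CGI-S could be carried into a later trial as the more responsive measure when part of the advantage comes from the entry rule. The fair comparators are the other anxiety measures, SCARED and CASI (of CASI the plan says: "These include 20 parent-rated items from the Child and Adolescent Symptom Inventory"). ABC-2 and PSQI measure behaviour and sleep, so a difference from them has other explanations.

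**Working it through.** **Plan's own figures.** Sample Size Considerations gives effect size 1.0, baseline to week 16 correlation 0.5, and 14 completers. SD of change = SD x sqrt(2(1 - 0.5)) = 1.0 SD. A two-sided paired t-test at 0.05 with n = 14 has 93.2% power for an effect of 1.0 (stated: greater than 90%). It has 79.0% power to rule out 1.0 when the truth is 0.2 (stated: nearly 80%). Both reproduce. The plan gives no figure for the comparison between scales.

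**Assumed inputs, not in the documents.** Normal scores; cut a from -1 to +0.5 SD of the unselected population (16% to 69% below it); between-scale correlation rho of 0.5, 0.7 or 0.9; baseline to week 16 correlation r of 0.5 to 0.8 in the unselected population, the same on both scales; equal true change of 1 unselected SD.

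**SD restriction.** Let l = pdf(a)/(1 - cdf(a)) and v = 1 + a·l - l². Baseline variance is v on the cut scale and 1 - rho²(1 - v) on the uncut scale. At a = 0 and rho = 0.5:

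- l = 0.798, v = 1 - 0.637 = 0.363, SD = 0.603
- uncut variance = 1 - 0.25 x 0.637 = 0.841, SD = 0.917
- ratio of effect sizes = 0.917/0.603 = 1.52

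This trial applies two minimums, which also restrict the uncut scales further. Simulating both at baseline (equal cuts, all correlations equal) gives SDs of 0.633 and 0.883, so the ratio falls to about 1.40.

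**Adding regression to the mean (one baseline cut).** Week 16 = r x baseline - 1 + noise of variance 1 - r². Mean decrease is 1 + (1 - r)·l on the cut scale and 1 + (1 - r)·rho·l on the uncut scale. At a = 0, rho = 0.5, r = 0.5:

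- cut: 1.399/0.603 = 2.32
- uncut: 1.199/0.917 = 1.31
- ratio 1.77 (1.63 at r = 0.8)

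**Change over SD of change, same case.** SD of change = sqrt((1 - r)² x baseline variance + 1 - r²).

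- cut: sqrt(0.25 x 0.363 + 0.75) = 0.917, index 1.399/0.917 = 1.53
- uncut: sqrt(0.25 x 0.841 + 0.75) = 0.980, index 1.199/0.980 = 1.22
- ratio 1.25 (1.10 at r = 0.8)

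The excess left is 0.25/0.77 = 32% at r = 0.5 and 0.10/0.63 = 16% at r = 0.8.

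**Ranges over all cuts (effect size of cut scale divided by that of uncut scale):**

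| Case | rho 0.5 | rho 0.7 | rho 0.9 |
|---|---|---|---|
| SD restriction only, both minimums at baseline | 1.17-1.54 | 1.11-1.36 | 1.04-1.14 |
| SD restriction only, one cut at screening only (screen-baseline correlation 0.8) | 1.11-1.29 | 1.08-1.20 | 1.03-1.08 |
| Planned measure with regression to the mean, one baseline cut | 1.23-2.13 | 1.16-1.74 | 1.06-1.28 |
| Change over SD of change, same model | 1.04-1.32 | 1.03-1.19 | 1.01-1.06 |

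Comparing the last two rows case by case, roughly 10% to 40% of the excess remains on the second index.

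**Against sampling noise.** With 14 completers the standard error of a difference between two planned effect sizes is about 0.47 (simulated without selection). In the model with regression to the mean, at rho = 0.5 and r = 0.5, a cut at -1 SD gives a spurious difference of 1.44 - 1.13 = 0.31, below one standard error. A median cut gives 2.32 - 1.31 = 1.01, about two.

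**The case against.** The case for leaving the plan alone has weight. The comparison is descriptive, sits in a 20-person open-label pilot, and is one of three criteria with no ranking rule. The size rests wholly on assumptions.

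The PARS half depends on a visit the protocol does not name. If only the screening score must qualify, the tilt is smaller and can vanish. For example, take a median cut and an uncut scale correlating 0.5 with the screening score. With screen-baseline correlation 0.7 the ratio is sqrt(1 - 0.25 x 0.637)/sqrt(1 - 0.49 x 0.637) = 1.11; with 0.5 it is 1.00.

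The CGI-S half can also be questioned. Aim 2 speaks of interviews and anxiety rating scales, and CGI-S is a single global rating. It also draws on the other measures, which points to higher correlations and smaller ratios.

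All of this limits the size and none of it reverses the direction. CGI-S is among the modelled outcomes, and its minimum is explicitly applied at baseline.

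A reader might also infer that change over SD of change hardly helps. That follows if the correlation of 0.5 is forced on each scale within the enrolled sample. At a median cut and rho 0.5 the ratios are then 1.34 against 1.60, leaving more than half of the excess. But this needs unselected correlations of about 0.69 on the cut scale and 0.53 on the other, so the two scales are no longer equally stable. The plan gives 0.5 for PARS only. With a common correlation most of the excess goes.

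**Conclusion.** The concern holds as a minor point: on the planned measure the scale comparison tends to favour PARS and CGI-S over SCARED and CASI. The direction rests on roughly normal scores. The size is not determined by the documents. It runs from a few per cent (high between-scale correlation, mild cut, or a screening-only PARS minimum) to something that could reorder scales (low correlation, strong cut at baseline). Confidence is medium.

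Two stronger readings are not supported. One is that the Aim 2 comparison is invalid, or that PARS or CGI-S will be wrongly preferred: no ranking rule exists, two other criteria count, and the tilt may be smaller than sampling noise. The other is that the sample size is wrong: its arithmetic reproduces and is unchanged by this point.

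Nor do the documents support the opposite reading, that the primary PARS analysis is untouched. Regression to the mean can enter the PARS change from baseline, and Aim 1's effect size is divided by the same restricted baseline SD.

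**What to change.** In the Statistical Analysis Plan, keep the planned effect size and add: *We will also report change divided by the SD of change for each scale. PARS and CGI-S are range-restricted by the entry criteria, so an advantage for them on the baseline-SD measure alone will not be taken as evidence of greater sensitivity to change.* State whether the SD of change comes from the fitted model or from completers' observed changes.

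In inclusion criterion 3, state the visit or visits at which the PARS minimum applies.

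A participant-level bootstrap interval for between-scale differences is optional. It would show how imprecise the comparison is but would not correct the tilt.

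The cost is a few sentences and a little extra analysis, with no new data or visits. The supplementary index reduces the tilt without removing it, so the interpretation sentence is needed alongside it.

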## Data Management:

When a participant is enrolled in the study, he or she will be assigned a unique identification number that is used to identify all data associated with that person, including hard copy, and computerized data. Data will be collected on hard-copy forms and then verified by data entry personnel. All of the hard copy research data is kept in locked file cabinets at the Lurie Center. Only the PI and primary research assistants will have access to these files, ensuring security of the hard copy records.

Once data is obtained, the clinician will review the form to make sure that all required items are completed and to clarify any ambiguous notations before giving it to the research assistant responsible for data entry. Several quality control measures are built into our computerized data management. Data entry forms have been designed that correspond to the measures used in this study. These forms are configured so that out-of-range values cannot be entered; data entry prompts appear in the correct order, including skipping questions when appropriate; and entered values cannot be inadvertently overwritten. Immediately after data entry, a series of logic check programs are run automatically, indicating any entered values that appear incorrect and the reason why. Logic check reports will be reconciled with the hardcopy and, if necessary, the clinician. Changes will then be entered, and the logic check programs executed again in order to detect any new errors resulting from the changed values. The process will continue until no further errors are detected by the logic check programs.

#### **Project Milestones:**

Year 1: The trial will be initiated after obtaining IRB approval. Eight subjects will enroll into the protocol.

Year 2: Trial enrollment continues. An additional 8 subjects will be enrolled into the protocol.

Year 3: Trial enrollment continues. The final 4 subjects will be enrolled into the protocol. Data will be analyzed.

#### **Schedule of Measures:**

Table 1. Schedule of Measures		Treatment Phase							
Measure	Screen	Baseline	Week						
			2*	4	6*	8	10*	12	16
Parent Ratings [1]									
Demographics	Х								
PARS [2]	Х	Х		Х		Х		Х	Х
SCARED [3]		Х		Х		Х		Х	Х
CASI Anxiety [4]		Х		Х		Х		Х	Х
ABC-2 [5]		Х		Х		Х		Х	Х
PSQI [6]		Х		Х		Х		Х	Х
Subject Assessments									
Height, Weight	Х								
Urine Pregnancy Test [7]	Х								

PARS**	Х	Х		Х		Х		Х	Х
SCARED**		Х		Х		Х		Х	Х
Stanford-Binet-5 (SB-5),	Х								
WASI-II [8], or									
Developmental Profile-4 (DP-									
4)									
Treating Clinician									
WS Diagnosis [9]									
Diagnostic Exam including	Х								
medical/psychiatric History									
Health/Behavior Review	Х								
Adverse Effects Review		Х	Х	Х	Х	Х	Х	Х	Х
CGI-Severity [10]	Х	Х							Х
CGI-Improvement [11]				Х		Х		Х	Х
Suicide Assessment [12] /	X*	X*	Х	X*	Х	X*	Х	X*	X*
C-SSRS* [13]									
Concomitant Treatments	X	Х	X	X		Х	Х	X	X
Concomitant Medications	X	Х	X	X		Х	Х	Х	X
*Telephone Visit: [1] Parent or primary caretaker ratings: [2] PARS = Pediatric Anviety Pating Scale: [3]									

\*Telephone Visit; [1] Parent or primary caretaker ratings; [2] PARS = Pediatric Anxiety Rating Scale; [3] SCARED = Screen for Child Anxiety Related Disorders; [4] CASI Anxiety = Child & Adolescent Symptom Inventory; [5] ABC-2 = Aberrant Behavior Checklist, Second Edition; [6] PSQI = Pittsburgh Sleep Quality Index; [7] Females of child-bearing potential only; [8] WASI-II = Weschler Abbreviated Scale of Intelligence, Second Edition; [9] genetic testing or clinical diagnosis; [10] CGI-S = Clinical Global Impression for Severity; [11] CGI-1 = Clinical Global Impression for Improvement [12] Suicide Assessment included in Adverse Effect Review; [13] Columbia-Suicide Severity Rating Scale (C-SSRS)\* will be administered to participant and/or parent if any positive suicidal ideation is reported during clinical assessment. Each visit following the first report of suicidal ideation will include the administration of the C-SSRS.; \*\* when subject's communication abilities allows

# F. ENVIRONMENT

The performance site is the Lurie Center in Lexington, Massachusetts. It serves as the major referral site for children, adolescents, and adults with autism and other neurodevelopmental disorders from throughout the State of Massachusetts, as well as neighboring states. Research is a major focus of the Center's mission. Approximately 20 patients with WS are seen annually for an initial evaluation, thus ensuring an adequate sample from which to recruit.

